28 JUN 2022

Version 5.0

Page: 9 of 149

	
Recruitment in the Essure arm is planned to continue as long as Essure is being implanted.
 
Enrollment in the laparoscopic tubal sterilization arm will be ceased once its enrollment reaches approximately 2:1 ratio laparoscopic tubal sterilization : Essure (anticipated).

Main variable(s)	
Section modified by Amendment 2 (Modification 7).
 
Pain: The proportion of subjects reporting AEs of chronic lower abdominal and / or pelvic pain after insertion of Essure System (ESS305) compared to the proportion of subjects reporting AEs of chronic lower abdominal and / or pelvic pain after laparoscopic tubal sterilization. Total incidence of pain events will be based on AE reporting.
 
Bleeding: The proportion of subjects reporting AEs of abnormal uterine bleeding after insertion of Essure System compared to the proportion of subjects reporting AEs of abnormal uterine bleeding after laparoscopic tubal sterilization. Total incidence of new onset or worsening abnormal bleeding events will be based on AE reporting.
 
Hypersensitivity / allergy: The proportion of subjects with adjudicated new onset or worsening allergic / hypersensitivity reactions (e.g., urticaria, rash, itching, as well as other symptoms that may be related to inflammation) in subjects wearing Essure inserts and in subjects undergoing laparoscopic tubal sterilization.
 
Autoimmune disorder: The proportion of subjects with adjudicated newly diagnosed or worsening autoimmune disorders in subjects wearing Essure inserts and in subjects undergoing laparoscopic tubal sterilization.
 
Proportion of subjects undergoing invasive gynecologic surgery after Essure placement (excluding second placement attempts); including Essure insert removal compared to the proportion of subjects undergoing invasive gynecologic surgery after laparoscopic tubal sterilization.

Time point / frame of measurement for primary variable(s)	
Section modified by Amendment 2 (Modification 17).
 
The main endpoints will be evaluated through 60 months of follow up after the procedure.

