Any unplanned gynecological procedures will be conducted during the Study Procedure Visit. The AE assessment, alternative contraception (type used) were added to the text for consistency with the Schedule of evaluations at the Study Procedure Visit. The SF-36 was removed from text at three months post-procedure, and AMSS and two intermenstrual bleeding questions added to the text, for consistency with the Schedule of PRO evaluations. Weight and vital signs are measured at each in-person visit.

Sections affected include:

- 9.2.1 – Screening period;
- 9.2.2 – Study procedure period;
- 9.2.2.6 – Three months post-procedure.

Modification 16

Removed post-procedure contact method.

Rationale:

Contact with subject post-procedure is no longer required to be via telephone. The type of contact can include telephone, visit, etc.

Sections affected include:

- 9.1 – Tabular schedule of evaluations;
- 9.2.2.3 – Second placement and conversion to a secondary procedure;
- 9.2.2.4 – One week post-procedure;
- 9.2.2.5 – Confirmation test (Essure group);
- 9.2.2.6 – Three months post-procedure.

Modification 17

Added 48-month contact, 60-month visit, and premature discontinuation (dropout) visit.

Rationale:

Per discussions with the FDA, the existing follow-up period was extended to 5 years. Text was added to clarify the procedure in cases of premature discontinuation (dropout) from the study.

Sections affected include:

- 2 – Synopsis – Test device, Duration of treatment; Methodology; Time point / frame of measurement for primary variable(s);
- 9.1 – Tabular schedule of evaluations;
- 9.2.2.9 – Thirty-six months post-procedure (± 4 weeks)
- 9.2.2.10 – Forty-eight months post-procedure (± 4 weeks)
- 9.2.2.11 – Sixty months post-procedure (-4 weeks, +1 week) (End of Study)
- 9.2.2.12 – Premature Discontinuation (Dropout) (new section)

Modification 18

Corrected name of End of Study form.

Rationale:

The Study Completion/Termination Visit form referenced in the original protocol should be the End of Study form.

Sections affected include:

- 9.2.2.11 – Sixty months post-procedure (± 4 weeks).

Modification 19

Amended baseline characteristics.

Rationale:

Eyeglasses have been added to the list of baseline characteristics.

Sections affected include:

- 9.3.3 – Other baseline characteristics.

Modification 20

Added device events to safety definitions.

Rationale:

Text for device events was missing from the original protocol.

Sections affected include:

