### **4.3 Handling of loss to follow-up, premature discontinuation, and censoring**

Subjects who leave the study before reaching the study completion assessment five years after start of the sterilization procedure will be included in the analysis populations, since the analyses are based on all subjects who attempt sterilization.

For subjects who attempt two sterilization methods, or have any hysterectomy (subtotal, total or radical), or have Essure complete removal using a salpingectomy, or device removal not accompanied by sterilization procedure, their data will be censored for analysis purpose on the earliest date of second sterilization method, hysterectomy surgery date, or Essure removal date, for the primary analysis.

Data will be collected for all the subjects until the end of study or early termination.

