## 6.4 Outcome endpoints and variables

The main objective of this observational study is to evaluate under routine clinical practice conditions the incidence of important treatment-emergent AEs under hysteroscopic sterilization (Essure) and laparoscopic tubal sterilization. An AE is considered as treatment-emergent when it starts or worsens on or after the index date and up to the date of subject withdrawal or the censoring date, as described in Sections 4.3 and 6.1.3.

The outcome endpoint and variables are presented in Table 2. The descriptive analysis will be performed for all the variables listed below and the comparative analysis will be performed only for the main endpoints.

For the main endpoints, the subject incidence (regardless of the time each subject is “at risk”) is the number of subjects with treatment-emergent events divided by the number of subjects at risk.

Laboratory evaluation results will be compared to their normal ranges. Any values out of normal ranges will be identified. The change from baseline for each laboratory parameter will also be presented for each post-baseline visit.

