#### **6.4.1 Subject Incidence**

The subject incidence is defined as the number of subjects with at least one event divided by the number of subjects at risk. Subject incidence will be calculated for each group. The risk difference between two groups will also be calculated. Its associated 95% CI will be derived based on normal approximation.

Additionally for the main endpoints, subject incidence and risk differences will be given for the following time intervals: Day 0, Day 1-7, Day 8-30, Day 31-90, Day 91-180, Day 181-365, Day 366-730, > Day 730.

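### The interval table in SAP 6.4.1 pools Years 3 to 5 in one crude proportion, so it gives no group difference by year after Day 730 and could be distorted if censoring differs by group

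*SAP*

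**What the plan says.** SAP 6.4.1 defines the measure: "The subject incidence is defined as the number of subjects with at least one event divided by the number of subjects at risk". It also plans the between-group risk difference, and of that difference it says: "Its associated 95% CI will be derived based on normal approximation". For the main endpoints, incidence and risk difference are additionally given for Day 0, Day 1-7, 8-30, 31-90, 91-180, 181-365 and then "Day 366-730, > Day 730".

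SAP 6.4 gives the same ratio for the main endpoints (it "is the number of subjects with treatment-emergent events divided by the number of subjects at risk") and states that it applies regardless of how long each woman is at risk. Neither section says whether, within an interval, the women at risk are the whole analysis set or only those still followed when the interval opens.

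On duration the documents agree. The protocol synopsis states: "The main endpoints will be evaluated through 60 months of follow up after the procedure". SAP 4.3 refers to a "study completion assessment five years after start of the sterilization procedure". The Amendment 2 log records, as history only, that "the existing follow-up period was extended to 5 years".

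In the primary analysis (SAP 4.3 and 6.1.3), data are censored at a second sterilization method, hysterectomy, Essure removal or the start of hormonal manipulation.

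**The concern.** The first two years have seven rows and the last three years have one. The cut points would suit a 36-month study, where the final class would last one year.

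Two things follow. First, a risk that falls after Year 2 and one that rises towards Year 5 can produce the same entry. Detection of events also changes inside the class. Under Protocol Table 9-2 the pain and bleeding questionnaires, whose thresholds prompt adverse-event assessment, are quarterly to Month 36 and then given only at Months 48 and 60.

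Second, a crude proportion over three years counts fewer events in a group whose women leave observation sooner. Essure removal is a censoring event that only women with inserts can have, so unequal censoring is plausible. At stake is the only planned table of group differences by period, in a safety study with five years of follow-up.

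**Working it through.** The plan states no sample size, event rate or censoring rate, so it has no figure to reproduce. The interval lengths follow from the documents. The hazards below are assumptions.

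**1. Size of the open class.** Five years = 5 × 365.25 ≈ 1826 days. 1826 - 730 = 1096 days, and 1096 / 1826 = 60%. With 36 months (1096 days) it would be 366 days, or 33%.

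**2. Loss of timing, with no censoring at all.** Assume yearly hazards of 8%, 4%, 2% in Years 3, 4, 5, or the reverse. Both give 1 - exp(-0.14) = 13.1% in the pooled class. By year they give 7.7%, 3.9%, 2.0% and 2.0%, 3.9%, 7.7%.

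**3. Distortion if censoring differs.** For a constant event hazard h and censoring hazard c, among women at risk when the class opens:

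- true risk over t years = 1 - exp(-ht)
- crude proportion = h/(h+c) × (1 - exp(-(h+c)t))

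Example with t = 3, h = 0.05 in both groups, c = 0.20 (Essure) and 0.05 (laparoscopic):

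- Essure: 0.05/0.25 × (1 - exp(-0.75)) = 0.1055
- Laparoscopic: 0.05/0.10 × (1 - exp(-0.30)) = 0.1296
- Difference: -2.41 points, where the true difference is 0

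Crude three-year percentages, Essure vs laparoscopic, with the false difference in points:

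| Event hazard per year, both groups | True risk | Censoring 5% vs 5% | Censoring 10% vs 5% | Censoring 20% vs 5% |
|---|---|---|---|---|
| 2% | 5.82 | 5.41 vs 5.41 (0) | 5.04 vs 5.41 (-0.37) | 4.39 vs 5.41 (-1.02) |
| 5% | 13.93 | 12.96 vs 12.96 (0) | 12.08 vs 12.96 (-0.88) | 10.55 vs 12.96 (-2.41) |
| 10% | 25.92 | 24.16 vs 24.16 (0) | 22.56 vs 24.16 (-1.60) | 19.78 vs 24.16 (-4.38) |

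The sign follows the group that loses more follow-up. With 5% vs 10%, the differences are +0.37, +0.88 and +1.60.

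**4. Effect of the undefined denominator.** If the denominator is the whole set and the same hazards also apply in Years 1 and 2, each crude value is multiplied by exp(-2(h+c)). The false differences become -0.7 to -2.8 points (10% vs 5%) and -1.9 to -7.0 points (20% vs 5%).

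**5. Yearly classes.** With t = 1 in the example: 4.42% vs 4.76%, or -0.33 points per year and about -1.0 over three years. The ratio moves from 0.81 to 0.93. The distortion is smaller but still present.

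**6. Other planned outputs after Day 730.**

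- Exposure-adjusted incidence (6.4.2): a group difference with 95% CI, but one rate per group over the whole risk period.
- Kaplan-Meier (6.4.3): tables and figures of the time course, with no group difference at a stated time.
- Cox (6.4.4): a treatment hazard ratio, with no period-specific effect specified.
- Sensitivity analysis (6.8): ignores censoring events, but changes no intervals and leaves dropout in place.

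**The case against.** The interval table is an additional display in a plan that calls itself exploratory and descriptive. Time at risk is already handled elsewhere for the same endpoints: Kaplan-Meier and Cox allow for censoring, the exposure-adjusted rate uses time at risk, and the analysis in 6.8 removes censoring by removal and hysterectomy. A reader might infer from the interval table alone that unequal follow-up is ignored, or that the late time course is lost. Neither is so, and this part of the objection stands. What it leaves open is narrower: none of these outputs gives a group difference by year after Day 730.

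A reader might also infer that the table is biased. The documents do not show that. They give no censoring rate for either group, and equal censoring leaves the risk difference at zero when the hazards are equal.

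Nor does more censoring mean fewer counted events for every main endpoint. Under SAP Table 4 and the text below it, hysterectomy and Essure removal by salpingectomy, hysterectomy or cornual resection are themselves invasive-surgery events, so more of them raise that group's incidence.

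Finally, it is tempting to say that follow-up was extended in order to study late events. The amendment log attributes the extension only to discussions with the FDA.

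**Conclusion.** The gap is real and minor. It lies in the presentation of late risk differences and is not an error in the time-to-event analyses. That Years 3 to 5, about 60% of follow-up, share one class follows directly from the documents, as does the loss of timing within it.

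The distortion is conditional. It runs from about -0.4 to -4.4 points under the assumed unequal censoring, with women at risk at Day 730 as denominator, constant hazards, and censoring independent of the event. It is zero under equal censoring and changes sign if the laparoscopic group is censored more. It applies to endpoints other than invasive surgery.

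**What to change.** In SAP 6.4.1, replace the open class by Day 731-1095, Day 1096-1460 and Day 1461 to end of study. State that the denominator in each interval is the women still at risk at its start.

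In SAP 6.4.3, add Kaplan-Meier risk differences between groups with 95% CI at 36, 48 and 60 months. This is needed because yearly classes reduce the effect of unequal censoring without removing it. The Kaplan-Meier differences remove it only if censoring is non-informative, so they should be read beside the sensitivity analysis in 6.8.

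The cost is two more rows per interval table and three more time points, with no new data. Each late interval will hold fewer events, so its confidence interval will be wider.

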#### **6.4.2 Exposure-adjusted subject incidence**

The exposure-adjusted subject incidence is defined as the number of subjects with at least one event divided by the total time at risk. For the subject who has at least one event, the risk duration is from the index date to the date of the first event. For the subject who has no events reported, the risk duration is from the index date to the censoring date or end of study date. The exposure adjusted incidence will be calculated for each group. The difference between two groups and its associated 95% CI will be calculated using the method proposed by Liu et.al (2006) [1].

#### **6.4.3 Kaplan-Meier estimates**

Kaplan-Meier estimates for the main endpoints will be given in tables and figures describing the time course until the first event of interest. Subjects who did not experience the event until end of observation are right-censored, see also Section 6.1.3.

Confidence intervals are based on asymptotic method for standard error estimation by Greenwood (1926) [2].

The x-axis of the Kaplan-Meier figures will be restricted to the period in which at least 10% of the subjects are at risk as suggested by Pocock et al. (2002) [3].

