## **2 Study objectives**

The study has the following objectives:

- To evaluate the proportion of subjects who experience new onset or worsening chronic lower abdominal and / or pelvic pain who have undergone Essure placement (anyone who has had an attempt at placement defined as an insert that was placed in the operating channel of the hysteroscope will be included in the analysis, regardless of whether or not they are relying on Essure for contraception) compared to the proportion of subjects who had an attempt at laparoscopic tubal sterilization (defined as anyone who has had an incision or puncture of the skin, regardless of whether or not sterilization was successfully completed), and to better characterize these reported outcomes and identify pre-procedural and procedure-related characteristics that may be related to their occurrence.
- To evaluate the proportion of subjects who experience new onset or worsening abnormal uterine bleeding who have undergone Essure placement (as defined above) compared to the proportion of subjects who have undergone laparoscopic tubal sterilization (as defined above)

and to better characterize these reported outcomes and identify pre-procedural and procedure-related characteristics that may be related to their occurrence.

- To evaluate the proportion of subjects who undergo gynecologic or related surgical intervention (including “insert removal” and hysterectomy) after undergoing hysteroscopic sterilization with Essure versus laparoscopic tubal sterilization.
- To identify the proportion of subjects who experience new onset or worsening allergic, hypersensitivity, or autoimmune-like reactions after Essure placement or laparoscopic tubal sterilization and to better characterize these reported outcomes and any characteristics that may be related to their occurrence.
- To collect data on patient reported outcomes in subjects who have undergone hysteroscopic or laparoscopic tubal sterilization procedures.
- To collect rates of adverse events (AEs) in subjects undergoing Essure placement or laparoscopic tubal sterilization

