### 6.1.3 Risk period definition

The safety outcomes analyzed are those occurring in the at-risk-period defined as the time from the index day (Day 0) until a specified censoring date as defined in Section 4.4. The censoring date is the earliest date of second sterilization method, hysterectomy surgery date, Essure removal date, or the date of hormonal manipulation start date for the primary analysis.

For some bleeding analyses the risk period will be restricted. For example, in the Essure group hormonal contraception is expected at least until the subjects are told to rely on Essure for permanent contraception. To have comparable risk periods in the two groups a similar restriction will be applied to the laparoscopic tubal sterilization group.

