**Table 2 - Outcome endpoints and variables collected during treatment**

	Endpoint/Variable
Main Endpoints	
 
Subjects reporting AEs of chronic lower abdominal and/or pelvic pain after sterilization procedure
 
Subjects reporting AEs of abnormal uterine bleeding after sterilization procedure
 
Subjects with reported allergic/hypersensitive reactions
 
Subjects with newly diagnosed autoimmune disorders
 

	Endpoint/Variable
	
 
Subjects undergoing invasive gynecologic surgery (e.g., device removal or hysterectomy) after sterilization procedure (excluding second Essure placement attempts)
 

Patient Reported Outcomes	
 
MOS SF-36 (Version 2) which includes eight distinct health domains (physical function, role-physical, bodily pain, mental health, role-emotional, social functioning, vitality, and general health perceptions) and physical component summary and mental component summary scores
 
PROMIS Scale V1.0—Pain Intensity 3a, raw score, T-Scores, percentages of subjects who had T-Scores more than 50 and 60
 
PROMIS Scale V1.0—Pain Interference 8a, raw score, T-Scores, percentages of subjects who had T-Scores more than 50 and 60
 
AMSS and two intermenstrual bleeding questions used to characterize bleeding in subjects undergoing Essure placement and laparoscopic tubal sterilization, total raw scores and individual score for each question, percentage of subject having total scores greater than 40
 
FSQ: to investigate if scores on this instrument (continuous and categorical) correlate with chronic pelvic pain over the course of the study
 
Supplemental PRO Questionnaires
 
Social Media Questionnaire
 

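### Abnormal uterine bleeding (AUB) is shown by Kaplan-Meier with hysterectomy censored; read as the proportion of women with AUB, 1-KM is somewhat too high wherever hysterectomy precedes a first AUB event

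*SAP*

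**What the plan says.** One of the objectives in SAP section 2 is "To evaluate the proportion of subjects who experience new onset or worsening abnormal uterine bleeding", compared between Essure and laparoscopic sterilization. SAP Table 2 lists the matching main endpoint: "Subjects reporting AEs of abnormal uterine bleeding after sterilization procedure".

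For the primary analysis, SAP 4.3 covers women with a hysterectomy of any extent, in either arm, among others: "their data will be censored for analysis purpose on the earliest date of second sterilization method, hysterectomy surgery date, or Essure removal date". SAP 6.1.3 repeats the rule as the end of the risk period: "The censoring date is the earliest date of second sterilization method, hysterectomy surgery date, Essure removal date". It then adds the start of hormonal manipulation.

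SAP 6.4.3 states: "Kaplan-Meier estimates for the main endpoints will be given in tables and figures describing the time course until the first event of interest". On women without the event it says: "Subjects who did not experience the event until end of observation are right-censored", with a cross-reference to 6.1.3. Neither document mentions competing risks or a cumulative incidence function.

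AUB is also summarised by crude subject incidence with a risk difference (6.4.1), an exposure-adjusted rate (6.4.2) and a Cox hazard ratio (6.4.4). Section 6.8 repeats the main-endpoint analyses on all data to the end of study, ignoring the censoring events.

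**The concern.** Kaplan-Meier assumes that a censored woman remains able to have the event at the rate seen in those still at risk. That is reasonable for a woman who moved away. It is not reasonable for uterine bleeding after hysterectomy: SAP Table 4 describes even the subtotal category as removal of the uterus. Hysterectomy before a first AUB event is a competing event, and censoring it makes 1-KM answer a different question from the one in the objective, namely how many women would have AUB if nobody had a hysterectomy. The SAP does not state that target.

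At stake is the comparison of the two curves. Protocol 9.2.2.2 lists hysterectomy among the methods of Essure removal, a route that the laparoscopic arm does not have, so the hysterectomy rates could differ. If they do, part of the gap between the curves, or its absence, would reflect surgery and not bleeding.

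**Working it through.** **Inputs.** From the documents: 5 years of follow-up, the censoring rules above and 1-to-1 matching (SAP 6.6.1). There is no stated sample size, AUB rate or hysterectomy rate, so there is no figure of the plan to reproduce. The rates and n below are assumptions.

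**Formulas.** Let l be the hazard of a first AUB event, m the hazard of hysterectomy before any AUB, and T = 5 years, with constant hazards.
- Planned display: 1-KM = 1 - exp(-lT).
- Proportion who actually have AUB: CIF = l/(l+m) × [1 - exp(-(l+m)T)].

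Here lT = -ln(1 - AUB%) and mT = -ln(1 - hysterectomy%).

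The direction does not depend on constant or independent hazards. The CIF accumulates the AUB hazard only over women free of both events, and that group is never larger than the survivor fraction that Kaplan-Meier uses.

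**Worked case, AUB 30% by 1-KM and AUB-free hysterectomy 10%.** lT = 0.3567 and mT = 0.1054, sum 0.4620. Free of both at 5 years: 0.70 × 0.90 = 0.63. CIF = (0.3567/0.4620) × 0.37 = 28.6%. The excess is 30.0 - 28.6 = 1.4 points. The binomial SE at n = 300 is √(0.2856 × 0.7144/300) = 2.61 points, so the excess is 0.55 SE.

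**One arm, AUB 30% by 1-KM:**

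| AUB-free hysterectomy | CIF | Excess (points) | In SE, n = 300 | In SE, n = 500 |
|---|---|---|---|---|
| 5% | 29.3% | 0.7 | 0.27 | 0.35 |
| 10% | 28.6% | 1.4 | 0.55 | 0.71 |
| 15% | 27.8% | 2.2 | 0.84 | 1.09 |

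**Between arms, equal AUB hazards (the curves show a difference of 0):**

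| 1-KM | Hysterectomy | Shift (points) | In SE, n = 300 per arm | In SE, n = 500 per arm |
|---|---|---|---|---|
| 30% | 10% vs 5% | 0.73 | 0.20 | 0.25 |
| 30% | 15% vs 5% | 1.47 | 0.40 | 0.51 |
| 20% | 15% vs 5% | 1.0 | 0.31 | 0.40 |

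These SEs ignore loss to follow-up, so the ratios are if anything too high.

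**Which hysterectomies count.** In a simulation where hysterectomy happened only after AUB (12.9% of women by 5 years), 1-KM and the true proportion agreed at 19.95%. Only AUB-free hysterectomies cause bias.

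**Which arm is affected more.** At similar AUB hazards, it is the arm with more AUB-free hysterectomies. In points the order can reverse: AUB 10% with hysterectomy 10% gives 0.50 points, while AUB 25% with hysterectomy 6% gives 0.72. The relative excess follows the hysterectomy rate almost alone: about 2.5, 5, 8 and 11% at 5, 10, 15 and 20% hysterectomy.

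**The other displays.** A simulation of 400,000 women (AUB 20%, hysterectomy 10%, an assumed 25% lost to follow-up) gave 20.0% by the planned 1-KM and 19.05% truly with AUB. Keeping hysterectomised women at risk, as 6.8 would, gave 19.04%. Crude incidence was 16.7%: not inflated by hysterectomy, but lowered by loss to follow-up.

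**The case against.** The strongest reply is that the SAP never presents 1-KM as the proportion with AUB. Section 6.4 defines the main-endpoint measure as crude subject incidence, and 6.4.1 gives that measure its risk difference and confidence interval; the curves describe the time course. This stands, and it limits the point to how the curves and their tables are read.

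Second, 6.8 follows women past hysterectomy and, if Kaplan-Meier is rerun there, comes very close to the cumulative incidence. This stands in part. Section 6.8 lifts every censoring rule at once, does not name Kaplan-Meier, is not labelled for this purpose and leaves the primary display unchanged.

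Third, the effect may be small. The study is exploratory, and protocol 9.6.1.6 expects too few pathology specimens for statistical comparison, which does not suggest frequent surgery. This stands as to size.

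Fourth, SAP Table 3 counts vaginal and genital haemorrhage and amenorrhoea as AUB, so a listed term is not strictly impossible after hysterectomy. This is true, but the objective concerns uterine bleeding.

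Finally, the censored curve could be defended as a hypothetical no-hysterectomy estimate. The SAP does not say so, and that reading would need hysterectomy to be unrelated to bleeding risk, which it does not argue.

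A reader might go further and infer that the Essure curve will be inflated more, or that the bias is always larger in the arm with more hysterectomies. The documents do not support either. They give no rates, listing hysterectomy as a removal method is not evidence of a higher rate, and the ordering in points also depends on the AUB hazards.

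**Conclusion.** The point holds as a minor-to-moderate improvement, not a major error. The direction is certain: 1-KM exceeds the proportion of women with AUB whenever hysterectomy precedes a first AUB event. The size rests on assumed rates. It stays under 1 point unless AUB-free hysterectomy reaches about 10% with AUB of 20% or more, and the between-arm shift is a fraction of a standard error at 300 per arm in the scenarios shown.

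It would be wrong to conclude that the AUB comparison as a whole is invalid. The risk difference in 6.4.1 does not carry this inflation, and the Cox model in 6.4.4 remains interpretable as a cause-specific hazard ratio. What needs correcting is the AUB curve and the 5-year percentage that readers will take from it.

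**What to change.** In SAP 6.4.3, for AUB:

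- Replace 1-KM, or at least accompany it, with the Aalen-Johansen cumulative incidence by arm, with hysterectomy and death as competing events.
- Report by arm the number and cumulative incidence of hysterectomies before a first AUB event.
- State that a hysterectomy done to remove Essure counts as the competing event, since it would otherwise share its date with the Essure-removal censoring rule.
- State that Essure removal by other means, second sterilization and the start of hormonal manipulation remain censoring events, so the curve is conditional on those rules.

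In SAP 6.4.4, label the AUB hazard ratio as cause-specific.

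The cost is SAP wording and a little more programming. No new data are needed: 4.3 already uses hysterectomy dates and 4.4.1 uses death dates. The displayed AUB proportion will be slightly lower than under 1-KM.
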